### **7.2.5 Sponsor Responsibility for Reporting Adverse Events**

All Adverse Events will be reported to regulatory authorities, IRB/IECs and investigators in accordance with all applicable global laws and regulations.

## **8.0 STATISTICAL ANALYSIS PLAN**

### **8.1 Statistical Analysis Plan Summary**

This section contains a brief summary of the statistical analysis plan for this trial. Full details are provided in the Statistical Analysis Plan (SAP) (Section 8.2).

The primary objective of this study is to identify the ORR of *PD-L1* gene-altered relapsed/refractory DLBCL patients to pembrolizumab, and to determine whether this is significantly higher than a historical control of unselected relapsed/refractory DLBCL patients treated with pembrolizumab on the KEYNOTE-013 study.

For the purposes of this clinical trial, the definition of relapsed/refractory disease includes patients who have experienced disease progression after receiving  $\geq 2$  lines of prior systemic therapy,  $\geq 1$  line of prior systemic therapy in those ineligible for or who have refused autologous stem cell transplantation, or patients who have received 1 line of prior therapy and have had primary refractory disease, or experienced a relapse within 12 months from initial diagnosis. The response assessment of patients enrolled on study will be determined using the LYRIC response criteria (1).

#### **8.1.1 Efficacy Analyses**

The full analysis set (FAS) population (defined as all subjects with a baseline disease burden assessment who receive at least one dose of study treatment) will serve as the primary population for the analyses of efficacy data in this trial. Subjects who withdraw prior to receiving any study drug will be considered non-evaluable. Subjects in the FAS population with missing outcomes data will be considered as non-responders. An exact 95% confidence interval (two-sided) for the response rate will be estimated based on the binomial distribution, along with a one-sided test of the null hypothesis (see 8.1.3). Secondary time-to-event efficacy endpoints including PFS, OS, and DOR will be assessed by Kaplan-Meier survival analyses, and 95% confidence intervals will be calculated using Greenwood's formula.

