#### **8.1.3 Power and Sample Size**

The sample size for this study was determined using a Simon two-stage design. We project an ORR of 15%, below which the response will be unacceptable to continue the development of *PD-L1* gene alterations as a biomarker of responsiveness to pembrolizumab based upon results

from unselected DLBCL patients enrolled on the KEYNOTE-013 study; an ORR of  $\geq 40\%$  will be considered worthy of further exploration of this biomarker. The null hypothesis that the ORR is  $< 15\%$  will be tested against the alternative hypothesis that the ORR is  $\geq 40\%$ . The sample size computations were performed assuming a 5% level of significance, 90% power, and an optimal two-stage design.

Using these criteria, a maximum of 29 FAS patients will be enrolled (more than 29 patients may need to be enrolled to obtain the full analysis set population if there are enrolled patients that fail to receive a dose of study medication). In the first stage, 13 patients will enter the study. If 2 or fewer respond, the study will be terminated early and declared to have a negative result. If 3 or more patients respond, enrollment will be extended to a total of 29 FAS patients. At Stage 2, the biomarker strategy will be declared effective and worthy of further testing if 8 or more patients respond.

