## **8.2.5 Statistical Methods**

### **8.2.5.1 Statistical Methods for Efficacy Analyses**

Efficacy results will be considered to be statistically significant if Type I error rates are less than 5% per the two-stage design criteria stated above. For the primary efficacy endpoint, the point estimate and 95% confidence interval will be provided using exact binomial distribution. Subjects in the primary analysis population (FAS) without response data will be counted as non-responders.

Exploratory objectives will be evaluated using a combination of comparative and descriptive statistics. For example, response rates between patients with and without *PD-L1* gene alterations will be compared using Fisher's exact test and nonparametric, Wilcoxon rank-sum tests will be performed to compare PD-L1 protein expression as assessed by immunohistochemistry (IHC) between responders and non-responders. Cox (50) regression models will be fit to determine whether other exploratory biomarkers are associated with PFS and OS, depending on the number of events observed.

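### The ORR estimate and exact 95% CI ignore the Simon stage-1 stop: the estimate is biased low, and at exactly 8/29 the CI includes the 15% null although the rule declares success

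*Combined protocol and SAP*

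**What the plan says.** Section 8.1.3 sets a Simon two-stage rule with a null ORR of 15% and a target of 40%, "assuming a 5% level of significance, 90% power, and an optimal two-stage design". Stage 1: "In the first stage, 13 patients will enter the study". The futility rule is: "If 2 or fewer respond, the study will be terminated early and declared to have a negative result". Otherwise enrolment continues to 29 patients in the full analysis set, and "At Stage 2, the biomarker strategy will be declared effective and worthy of further testing if 8 or more patients respond".

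For inference, Section 8.1.1 states: "An exact 95% confidence interval (two-sided) for the response rate will be estimated based on the binomial distribution, along with a one-sided test". The same sentence goes on to refer the test of the null hypothesis to Section 8.1.3. Section 8.2.5.1 ties statistical significance to a Type I error below 5% under the two-stage criteria, and then says that "the point estimate and 95% confidence interval will be provided using exact binomial distribution". Both sections count patients without response data as non-responders.

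The test is thus anchored to the two-stage design. The estimate and interval are described as plain exact binomial, with no mention of the first stage. No section says how the p-value is to be calculated, and no section makes exclusion of 15% from the interval a condition for success.

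**The concern.** The design controls error at 5% only because trials with 2 or fewer responders among the first 13 stop and cannot succeed. An ordinary binomial estimate and interval treat the final count as if 29 patients had been taken in one step. In addition, a two-sided 95% interval carries 2.5% per side, while the rule operates at one-sided 5%.

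The primary objective (Section 3.1) is to show an ORR significantly higher than 15%. If the trial ended at its success boundary, the report would declare success beside an interval that includes 15%. With no method named in advance, the choice of p-value and interval would then be made after the result was known. Separately, the reported ORR would understate the true rate on average.

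**Working it through.** **Inputs (Section 8.1.3).** p0 = 15%, p1 = 40%, n1 = 13, stop at 2 or fewer, n = 29 (16 more patients), success at 8 or more.

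**Notation.** b(x; m, p) is the binomial probability of x responders in m patients. The probability of reaching stage 2 and ending with s responders is f(s; p) = Σ b(x; 13, p) · b(s − x; 16, p), summed over x from 3 to min(13, s). The two-stage tail is S(s; p) = f(s; p) + f(s+1; p) + … + f(29; p).

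**1. The plan's design reproduces.**
- Type I error: S(8; 0.15) = 0.04999.
- Power: S(8; 0.40) = 0.907.
- Probability of stopping at stage 1 under 15%: 0.692. Expected sample size: 13 + 16 × (1 − 0.692) = 17.9.
- A search over designs with alpha at most 0.05 and power at least 0.90 returns this one as the optimal design.

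**2. The boundary result, 8/29 = 27.6%.**
- Two-stage one-sided p = S(8; 0.15) = f(8; 0.15) + S(9; 0.15) = 0.0296 + 0.0204 = 0.04999 before rounding. This is significant under the plan.
- Planned ordinary exact 95% CI: 12.7% to 47.2%. It contains 15%.
- Ordinary exact 90% CI: 14.5% to 44.3%. It still contains 15%, so matching the level alone does not restore agreement.
- Two-stage one-sided 95% lower bound, the p that solves S(8; p) = 0.05: 15.0005%. This agrees with the rule.
- Lower limit of a two-stage two-sided 95% CI, the p that solves S(8; p) = 0.025: 13.1%. This contains 15%, so the two-stage correction alone does not restore agreement either. Both changes are needed.

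**3. The next result, 9/29 = 31.0%.** Two-stage p = 0.0204; ordinary 95% CI 15.3% to 50.8%. Rule, p-value and interval agree, and they agree at every higher count.

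**4. How often the trial ends at exactly 8/29.** These are unconditional probabilities, f(8; p). The last column divides by S(8; p).

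| True ORR | f(8; p) | S(8; p) | Share of successes |
|---|---|---|---|
| 30% | 12.8% | 62.1% | 21% |
| 35% | 9.3% | 79.8% | 12% |
| 40% | 5.0% | 90.7% | 5.6% |

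**5. Bias of the observed proportion.** E = Σ b(x; 13, p) · x/13 for x = 0 to 2, plus Σ f(s; p) · s/29 for s = 3 to 29.

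| True ORR | E | Bias (points) |
|---|---|---|
| 20% | 17.50% | −2.50 |
| 30% | 28.06% | −1.94 |
| 40% | 39.15% | −0.85 |

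**6. Unbiased estimate (UMVUE) at 8/29.** With C for binomial coefficients and x from 3 to 8: Σ C(12, x−1) · C(16, 8−x) ÷ Σ C(13, x) · C(16, 8−x) = 1,076,504 ÷ 3,505,931 = 30.7%, against the observed 27.6%.

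**7. Sensitivity to the null.** Section 4.2.3.2.1 gives the historical ORR as 13%. Against 13%, the two-stage p at 8/29 is 0.024, and the planned 95% lower limit of 12.7% is still below the null.

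**The case against.** A reader might infer that the plan contradicts itself outright: success by the rule at 8/29, but not significant by its own test, because an ordinary binomial test gives P(X ≥ 8 | 29, 0.15) = 0.0586. The documents do not support this. Section 8.1.1 refers the test to 8.1.3, and 8.2.5.1 defines significance by the two-stage criteria. No section names a single-stage test, so 0.0586 is not a figure the plan would produce if followed.

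The strongest defence goes further:
- The interval is there for estimation, not decision. A two-sided 95% interval can include the null when a one-sided 5% test rejects; that is a difference in level.
- The bias is downward, so it cannot inflate an efficacy claim.
- The ordinary 95% interval is conservative under this design. Its coverage was at least 96% at the true rates checked between 10% and 50%.
- The mismatch is confined to one outcome, and a positive result leads only to further testing.

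All of this stands, and it keeps the point minor. It does not remove it. The estimate and interval are still those of a design the trial does not use. Level explains only part of the mismatch, since the ordinary 90% interval also includes 15%. The p-value method is also left for the reader to infer. With a boundary p of 0.04999, an analyst who ran a standard exact test would report the opposite conclusion.

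**Conclusion.** The point holds as a minor inconsistency in estimation and reporting that should be fixed. The Simon rule is correctly computed, Type I error is controlled, and 8/29 is significant under the plan. It would be wrong to conclude that the decision rule is faulty or that the trial could fail its own test at the boundary.

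The size is a downward bias of about 0.85 to 2.5 points over true ORRs of 40% down to 20%, and an interval that appears to contradict a declared success at exactly one outcome. That outcome has a 5.0% chance at the design alternative and 12.8% at a true ORR of 30%.

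The figures assume that both stages run at exactly 13 and 29 patients as planned, that patients respond independently with a common rate, and that missing responses count as non-response.

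**What to change.** In Sections 8.1.1 and 8.2.5.1:

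1. State that the Simon rule governs the conclusion, and that the one-sided p-value is calculated over the two-stage sample space (0.04999 at 8/29).
2. Report the UMVUE (30.7% at 8/29) or another named bias-adjusted estimate beside the observed proportion.
3. Report a two-stage-adjusted interval that includes the one-sided 95% lower bound, equivalently a two-sided 90% CI, to match the one-sided 5% test (lower limit 15.0% at 8/29). Name the method, for example Koyama–Chen or Jung–Kim.
4. Keep the ordinary exact 95% CI as a labelled descriptive line.
5. State that no two-sided 95% interval is a success criterion. Even the two-stage version would start at 13.1% at 8/29.

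The cost is SAP wording and a few lines of code, with no change to sample size or boundaries. The change should be made before the response count is known, because a method chosen after seeing 8/29 would be open to challenge.

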#### **8.1.2 Safety Analyses**

The FAS population will be employed for safety analyses which will be descriptive in nature.

#### **8.1.3 Power and Sample Size**

The sample size for this study was determined using a Simon two-stage design. We project an ORR of 15%, below which the response will be unacceptable to continue the development of *PD-L1* gene alterations as a biomarker of responsiveness to pembrolizumab based upon results

from unselected DLBCL patients enrolled on the KEYNOTE-013 study; an ORR of  $\geq 40\%$  will be considered worthy of further exploration of this biomarker. The null hypothesis that the ORR is  $< 15\%$  will be tested against the alternative hypothesis that the ORR is  $\geq 40\%$ . The sample size computations were performed assuming a 5% level of significance, 90% power, and an optimal two-stage design.

Using these criteria, a maximum of 29 FAS patients will be enrolled (more than 29 patients may need to be enrolled to obtain the full analysis set population if there are enrolled patients that fail to receive a dose of study medication). In the first stage, 13 patients will enter the study. If 2 or fewer respond, the study will be terminated early and declared to have a negative result. If 3 or more patients respond, enrollment will be extended to a total of 29 FAS patients. At Stage 2, the biomarker strategy will be declared effective and worthy of further testing if 8 or more patients respond.

## **8.2 Statistical Analysis Plan**

### **8.2.1 Responsibility of Analyses**

The statistical analysis of the data obtained from this study will be the responsibility of the Biostatistics Laboratory of the University of Chicago.

This trial is being conducted as an open-label study, i.e., subjects, investigators, and personell will be aware of subject treatment assignments after each subject is enrolled and treatment is allocated.

### **8.2.2 Hypotheses/Estimation**

Objectives and hypotheses of the study are stated in Section 3.0.

### **8.2.3 Analysis Endpoints**

#### **8.2.3.1 Efficacy Endpoints**

Efficacy endpoints that will be evaluated are listed below followed by the descriptions of the derivations of selected endpoints.

The primary efficacy endpoint is objective overall response rate (ORR), defined as the proportion of subjects meeting the LYRIC criteria for an objective response at any time during the study. Response for the primary analysis will be assessed by the investigator.

Key secondary endpoints include:

- Progression-free survival (PFS) – defined as the time from treatment administration to documented disease progression according to LYRIC criteria or death from any cause. Patients in response who elect to proceed to stem cell transplantation will be censored on the date of stem cell infusion.

- Overall survival (OS) – defined as the time from treatment administration to death from any cause.
- Duration of response (DOR) – defined as the time from the first documented complete or partial response to disease progression or death.

## **8.2.4 Analysis Populations**

### **8.2.4.1 Efficacy Analysis Populations**

The Full Analysis Set (FAS) population will serve as the primary population for the analysis of efficacy data in this study. The FAS population consists of all allocated subjects who:

- Receive at least one dose of study treatment, and
- Have a baseline disease assessment

## **8.2.5 Statistical Methods**

### **8.2.5.1 Statistical Methods for Efficacy Analyses**

Efficacy results will be considered to be statistically significant if Type I error rates are less than 5% per the two-stage design criteria stated above. For the primary efficacy endpoint, the point estimate and 95% confidence interval will be provided using exact binomial distribution. Subjects in the primary analysis population (FAS) without response data will be counted as non-responders.

Exploratory objectives will be evaluated using a combination of comparative and descriptive statistics. For example, response rates between patients with and without *PD-L1* gene alterations will be compared using Fisher's exact test and nonparametric, Wilcoxon rank-sum tests will be performed to compare PD-L1 protein expression as assessed by immunohistochemistry (IHC) between responders and non-responders. Cox (50) regression models will be fit to determine whether other exploratory biomarkers are associated with PFS and OS, depending on the number of events observed.

### **8.2.5.2 Statistical Methods for Safety Analyses**

Safety and tolerability will be assessed by clinical review of all relevant parameters including adverse events (AEs), laboratory tests, and vital signs.

Summary statistics (counts, percentage, mean, standard deviation, etc.) will be provided for the safety endpoints as appropriate. The 95% confidence interval for the incidence rate of grade 2 or higher adverse events with an immune etiology and incidence rate of Grade 4/5 AEs will be provided as appropriate.

### **8.2.5.3 Summaries of Baseline Characteristics, Demographics, and Other Analyses**

#### **8.2.5.3.1 Demographic and Baseline Characteristics**

Baseline characteristics will be assessed by the use of tables and/or graphs. No statistical hypothesis tests will be performed on these characteristics. The number and percentage of subjects screened, allocated, the primary reasons for screening failure, and the primary reason for discontinuation will be displayed. Demographic variables (e.g., age, gender), baseline characteristics, primary and secondary diagnoses, and prior and concomitant therapies will be summarized by descriptive statistics or categorical tables.

#### **8.2.6 Compliance (Medication Adherence)**

A day within the study will be considered an On-Therapy day if the subject receives any dose of study medication. The number of Days Should be on Therapy is the total number of days from the first day of study medication to the date of the last dose of study medication. For each subject, percent compliance will then be calculated using the following formula:

$$\text{Percent Compliance} = \frac{\text{Number of Days on Therapy}}{\text{Number of Days Should be on Therapy}} \times 100$$

Summary statistics will be provided on percent compliance for the FAS population.

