## 5.2 Trial Treatments

The treatment to be used in this trial is outlined below in Table 2

Table 2. Trial Treatment

Drug	Dose/Potency	Dose Frequency	Route of Administration	Regimen/Treatment Period	Use
Pembrolizumab	200 mg	Q3W	IV infusion	Day 1 of each 3 week cycle	Experimental

Trial treatment should begin on or as close as possible to the day of allocation.

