### 5.2.1 Timing of Dose Administration

Trial treatment should be administered on day 1 of each cycle after all procedures/assessments have been completed as detailed on the Trial Flow Chart (Section 6.0). Trial treatment may be administered up to 3 days before or after the scheduled day 1 of each cycle due to administrative reasons.

All trial treatments will be administered on an outpatient basis.

Pembrolizumab 200 mg will be administered as a 30 minute IV infusion every 3 weeks. Sites should make every effort to target infusion timing to be as close to 30 minutes as possible. However, given the variability of infusion pumps from site to site, a window of -5 minutes and +10 minutes is permitted (i.e., infusion time is 30 minutes: -5 min/+10 min).

The Pharmacy Manual contains specific instructions for the preparation of the pembrolizumab infusion fluid and administration of infusion solution.

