## **5.6 Participant Withdrawal/Discontinuation Criteria**

Participants may discontinue study treatment at any time for any reason, and may also be discontinued from study treatment at the discretion of the investigator should any untoward effect occur. In addition, a participant may be discontinued from study treatment by the investigator or sponsor if study treatment is inappropriate, the trial plan is violated, or for administrative and/or other safety reasons. Specific details regarding procedures to be performed at study treatment discontinuation are provided in Section 7.1.4 – Other Procedures.

A participant must be discontinued from study treatment but continue to be monitored in the study for any of the following reasons:

- The participant or participant's legally acceptable representative requests to discontinue study treatment
- Confirmed radiographic disease progression outlined in Section 7.1.2.6
- Any progression or recurrence of any malignancy, or any occurrence of another malignancy that requires active treatment
- Unacceptable adverse events as described in Section 5.2.2
- The participant has a medical condition or personal circumstance which, in the opinion of the investigator and/or sponsor, placed the participant at unnecessary risk from continued administration of study treatment.
- The participant has a confirmed positive serum pregnancy test
- Noncompliance with study treatment or procedure requirements
- Recurrent Grade 2 pneumonitis
- Discontinuation of treatment may be considered for participants who have attained a confirmed complete response (CR) and have been treated for at least 8 cycles (at least 24 weeks), receiving at least 2 doses of pembrolizumab beyond the date when the initial CR was declared. These participants may be eligible for second course treatment described in Section 5.2.3.
- The participant is lost to follow-up
- Completion of 35 treatments (approximately 2 years) with pembrolizumab

Note: The number of treatments is calculated starting with the first dose. Participants who stop the combination or pembrolizumab after receiving 35 doses may be eligible for retreatment if they progress after stopping study treatment provided they meet the requirements detailed in Section 5.2.3. Participants may be retreated in the Second Course Phase (Retreatment) for up to an additional 17 cycles (approximately 1 year).

- Administrative reasons

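### The percent compliance formula divides infusion days by calendar days, so a fully adherent patient with two or more on-schedule doses scores between about 5% and 10%

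*Combined protocol and SAP*

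**What the plan says.** Section 8.2.6 (Compliance) builds percent compliance from two counts.

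- **Numerator.** "A day within the study will be considered an On-Therapy day if the subject receives any dose of study medication". A day without a dose therefore does not count.
- **Denominator.** The days on which the subject should be on therapy are the "total number of days from the first day of study medication to the date of the last dose of study medication".

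The ratio is multiplied by 100, and "Summary statistics will be provided on percent compliance for the FAS population".

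The dosing schedule is in Section 5.2. Table 2 gives treatment on "Day 1 of each 3 week cycle", and Section 5.2.1 says "Pembrolizumab 200 mg will be administered as a 30 minute IV infusion every 3 weeks". Section 5.2.1 also allows a window of 3 days either side of the scheduled day. Section 5.6 ends initial treatment at 35 doses. Under Section 8.2.4.1 the FAS requires only one dose and a baseline disease assessment, so one-dose patients enter the summary.

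Two other sections touch on the subject. Section 7.1.1.8 compares the volume infused with the volume prepared at each administration. Section 8.2.7 defines extent of exposure as the number of cycles with a dose.

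**The concern.** The formula fits a drug taken every day, where each day on treatment should carry a dose. Here only one day in each 21-day cycle can enter the numerator, while all 21 enter the denominator. A patient who receives every infusion on time would be tabulated at a few percent.

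The denominator also closes at the last dose actually given. Doses that were due after that date but not given leave no trace, and a shorter course produces a higher score.

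At stake is the planned FAS compliance table. Applied literally, the prespecified definition produces a figure that no reader can take as adherence. The statistician would then either have to report it or replace it after seeing the data.

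**Working it through.** The plan states no compliance figure to reproduce, so the check applies the formula to the plan's own schedule.

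**Inputs**
- Dosing interval: 21 days (Sections 5.2 and 5.2.1)
- Full initial course: 35 doses (Section 5.6)
- Numerator and denominator: as defined in Section 8.2.6

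**Formula.** For k doses given exactly on schedule, the numerator is k. Section 8.2.6 does not say whether both end days are counted, so both counts are shown:
- both end days counted: 100 × k / [21(k − 1) + 1]
- simple date difference: 100 × k / [21(k − 1)]

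**Results for a fully adherent patient**

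| Doses k | Both end days counted | Simple date difference |
|---|---|---|
| 1 | 1/1 = 100% | 1/0, undefined |
| 2 | 2/22 = 9.09% | 2/21 = 9.52% |
| 4 | 4/64 = 6.25% | 4/63 = 6.35% |
| 8 | 8/148 = 5.41% | 8/147 = 5.44% |
| 17 | 17/337 = 5.04% | 17/336 = 5.06% |
| 35 | 35/715 = 4.90% | 35/714 = 4.90% |

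As k grows under full adherence, both versions approach 1/21 = 4.76%.

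**Effect of the dosing window.** Allowing 3 days at each end, the 35-dose denominator runs from 709 to 721 days. The score then runs from 35/721 = 4.85% to 35/709 = 4.94%, so the window does not explain the low values.

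**Does the score respond to missed doses?** Take 18 scheduled doses with 12 given, including the first and last. The span is 21 × 17 + 1 = 358 days. The score is 12/358 = 3.35%, against 18/358 = 5.03% for all 18. The direction is right but the scale is not: 12 of 18 is 66.7%.

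**Doses missed at the end.** Suppose 4 doses fall due before treatment is discontinued and only the first 2 are given. The score is 2/22 = 9.09%. A patient given all 4 scores 4/64 = 6.25%. On doses received over doses scheduled, the two would score 2/4 = 50% and 4/4 = 100%.

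**Effect on a summary mean.** As an illustration with both end days counted, take 28 patients with 17 on-time doses and one patient with a single dose. The mean is (28 × 5.04 + 100)/29 = 8.3%, although none of the 29 missed a scheduled dose while on treatment.

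**The case against.** The strongest reply is that little depends on this table. Percent compliance defines no analysis set, sets no threshold and enters no test. The FAS, the response endpoint, the non-responder rule for missing outcomes and the two-stage decision are all defined without it. Infusions are given and witnessed by staff, the odd values would be obvious once tabulated, and a sensible measure could be recalculated from dosing dates. All of this stands, and it limits the severity.

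A second reply is that adherence and exposure are covered elsewhere. This stands in part. Section 8.2.7 does summarise cycles dosed, so a reader should not infer that the trial cannot describe exposure. But that count has no scheduled denominator. The volume check in Section 7.1.1.8 concerns only doses that were given, so it cannot reveal an omitted one. Neither repairs the formula.

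Three stronger readings are tempting and go too far:

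- **That the score tends to 1/21 whatever the adherence.** That limit needs full adherence. If a fraction a of scheduled doses is given, the limit is a/21, and the 12-of-18 example falls below it.
- **That patients are ranked backwards in general.** The inversion concerns how long patients are treated and doses missed after the last one given. Among patients with the same first-to-last span, fewer doses correctly give a lower score.
- **That a one-dose patient certainly scores 100%.** This requires both end days to be counted, which Section 8.2.6 does not say. Otherwise the score is undefined.

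**Conclusion.** The formula is wrong as written for a drug infused once every three weeks. Under perfect adherence it gives 9.1% at 2 doses (9.5% on a simple date difference), falling to 4.9% at 35. At one dose it gives either 100% or a division by zero. It reacts to doses missed between the first and last, but on a compressed scale dominated by treatment duration, and it ignores doses missed after the last one given. It cannot be read as percent adherence.

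These figures assume doses exactly 21 days apart; the permitted window barely moves the 35-dose result. The conclusion does not depend on how end days are counted, except for the form of the one-dose failure.

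Severity is minor. A reader might infer that a faulty compliance measure weakens the efficacy conclusion, but the documents give it no role in the response-rate test or the two-stage rule. Only a descriptive FAS summary is affected.

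**What to change.** Replace the definition in Section 8.2.6 with: percent compliance = doses received ÷ doses scheduled from first dose to treatment discontinuation × 100. A fully adherent patient then scores 100% at any duration (2/2, 17/17, 35/35), the one-dose case is defined, and doses missed before discontinuation count even when no later dose is given.

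The text should also state which date closes the schedule, and whether doses withheld under the protocol's own rules stay in the denominator, are removed from it, or are shown separately. These are analysis definitions and change no treatment rule.

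Relative dose intensity (amount received per unit time over the planned 200 mg per 3 weeks) would also show delays. It is an optional addition, not needed to correct the error.

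The cost is a few lines of SAP wording. The new measure needs dosing dates, which the existing formula already uses, and the planned schedule. Sample size, visits and the primary analysis do not change.
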